### Statistical Considerations

There will be an interim statistical analysis following the data collection of the first 30 subjects. The final analysis for the Vital Detect blood pressure monitor will contain no fewer than 85 subjects resulting in a minimum of 255 paired observations.

All data from a subject shall be excluded if any two reference systolic blood pressure determinations differ by more than 12 mmHg or if any two reference diastolic blood pressure determinations differ by more than 8 mmHg. If an individual subject is unstable during the period of the test, two valid consecutive determination pairs may be used. No more than 10% individual subjects may have fewer than three valid

Clinimark [name], USA Site 001	TITLE: Multiparameter Monitor Non-Invasive Blood Pressure Validation Study Clinimark Study ID#: PR2019-329 Principal Investigator: [name]	DOCUMENT NUMBER PR# 2019-329 SHEET 10 of 22	REV 1
---	---	--	-------

determinations. Therefore at least 90% of the subjects will contribute 3 paired observations, if necessary the balance of the data will be added from additional subjects.

Data analysis and demographics will be presented in the final report

The sphygmomanometer-under-test shall meet the following two criteria.

a) Criterion 1

For systolic and diastolic blood pressures, the mean error of determination,  $x_n$ , of the  $n$  individual paired determinations of the sphygmomanometer-under-test and the reference sphygmomanometer for all subjects shall be  $\leq \pm 5,0$  mmHg, with a standard deviation,  $s_n$ ,  $\leq 8,0$  mmHg when calculated according to Equation (1) and Equation (2):

The observers' individual values of each determination shall be averaged to create the reference blood pressure determination.

$$\bar{x}_n = \frac{1}{n} \times \sum_{i=1}^n (p_{sut_i} - p_{ref-sq_i}) \quad (1)$$

$$s_n = \sqrt{\frac{1}{n-1} \times \sum_{i=1}^n (x_i - \bar{x}_n)^2} \quad (2)$$

where

$x_n$  is the mean error;

$p_{sut_i} - p_{ref-sq_i} = x_i$  difference between the  $i$ th paired blood pressure determination (sphygmomanometer-under-test – reference sphygmomanometer);

$n$  is the number of determinations.

$i$  is the index of the individual element

$p_{ref-sq_i}$  is the REFERENCE BLOOD PRESSURE for the  $i$ th DETERMINATION as calculated according to Formula (3);

$\bar{x}_n$  and  $s_n$  shall be calculated and expressed to at least 0.1 mmHg (0.01 kPa).

The REFERENCE BLOOD PRESSURE,  $p_{ref-sq_i}$ , (the observers' DETERMINATIONS with the REFERENCE SPHYGMOMANOMETER) shall be the average of the preceding and following REFERENCE BLOOD PRESSURES.

$$p_{ref-sq_i} = \frac{1}{4} \times (p_{ref_{i,1}} + p_{ref_{i,2}} + p_{ref_{i+1,1}} + p_{ref_{i+1,2}}) \quad (3)$$

where

$p_{ref_{i,1}}$  is the BLOOD PRESSURE determined by observer 1 for the  $i$ th DETERMINATION;

$p_{ref_{i,2}}$  is the BLOOD PRESSURE determined by observer 2 for the  $i$ th DETERMINATION.

EXAMPLE  $n = 255$  for paired blood pressure measurements for a 85 subject study.

b) Criterion 2

For the systolic and diastolic blood pressures for each of the  $m$  subjects, the standard deviation,  $s_m$ , of the averaged paired determinations per subject of the sphygmomanometer-under-test and of the reference

Clinimark [name], USA Site 001	TITLE: Multiparameter Monitor Non-Invasive Blood Pressure Validation Study Clinimark Study ID#: PR2019-329 Principal Investigator: [name]	DOCUMENT NUMBER PR# 2019-329 SHEET 11 of 22	REV 1
---	--	---	-----------------

sphygmomanometer, shall meet the criteria listed in Table 1 when calculated according to Equation (4).

$$s_m = \sqrt{\frac{1}{m-1} \times \sum_{j=1}^m (x_j - \bar{x}_n)^2} \quad (4)$$

where

$\bar{x}_n$  is the mean error over all subjects (see Equation 1);

$m$  is the number of subjects;

$j$  is the index for the individual element

$x_j$  is calculated from Equation (4).

$$x_j = \frac{1}{d} \times \sum_{k=1}^d (p_{syst_j,k} - p_{ref-sq_j,k}) \quad (5)$$

where

$d$  is the number of determinations per subject.

$k$  is the index for the individual elements

$p_{ref-sq_j,k}$  is the REFERENCE BLOOD PRESSURE calculated according to Formula (6)

$$p_{ref-sq_j,k} = \frac{1}{4} \times (p_{ref_{j,k,1}} + p_{ref_{j,k,2}} + p_{ref_{j,k+1,1}} + p_{ref_{j,k+1,2}}) \quad (6)$$

EXAMPLE  $m = 85$  for a sphygmomanometer intended for use in participants (an 85 subject study).

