Phase 1 will enroll a minimum of 30 qualified subjects into the study. Two trained observers will listen to the Korotkoff sounds at the brachial artery of the arm. The reference blood pressure measurements by the observers will be performed sequentially with the device under test. The device under test memory will be cleared prior to the next determination. In some cases, this may mean powering down the device to clear the previous readings. The observers will complete 1 or 2 initial baseline blood pressure measurements and then 3 to 8 paired NIBP measurements to be collected for the Accuracy evaluation will follow. Any pair of observers' determinations with a difference greater than 4 mmHg shall be excluded. If any determinations are excluded, additional pair(s) of determinations shall be taken to ensure that the needed number of valid test-reference pairs is collected (up to a maximum of 8 paired readings). In some cases, it may be that only 2 valid paired readings are achieved. This protocol allows for up to 10% of the subjects to have 2 valid paired observations (90% or more will contribute 3 paired observations). In this case, additional subjects shall be used to complete the minimum number of paired observations. A minimum of 85 valid paired NIBP measurements is needed for the final Accuracy analysis. The blood pressure measurements will be such that reference cuff measurements will be alternated with the device under test measurement. The auscultator will wait a minimum of 60 seconds between each blood pressure determination. Each observer's recording of observations of the reference sphygmomanometer shall not be visible to the other observer. The observers will record the exact measurement heard during auscultation and will not round the blood pressure readings. The readings of the sphygmomanometer-under-test shall not be visible to either of these observers. Each subject test is expected to take up to 60 minutes for the enrollment / data collection process.

Clinimark [name], USA Site 001	TITLE: Multiparameter Monitor Non-Invasive Blood Pressure Validation Study Clinimark Study ID#: PR2019-329 Principal Investigator: [name]	DOCUMENT NUMBER PR# 2019-329 SHEET 7 of 22	REV 1
---	--	--	-----------------

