8. Record device information for tracking. (manufacturer, model #, serial or lot, hardware / software control info) on the Case Report Form (CRF).
9. Measure the circumference of the upper arm at the midpoint and place the appropriate sized reference blood pressure cuff on the bicep of the subject.
10. Attach the reference sphygmomanometer to the connector hose on the appropriate port on the reference blood pressure cuff.
11. Make sure the observers for the reference sphygmomanometer are positioned at a height level with the center of the manometer and within 15° from the centerline of the mercury tube (if used) so that parallax errors are avoided.
12. Both observers shall make an initial baseline reference blood pressure determination using a dual stethoscope. The last audible Korotkoff sound, fifth phase or K5, will be used for the diastolic blood pressure determination. Record which Korotkoff sound was used on the CRF. Record the baseline reference blood pressure reading on the CRF.
13. Apply the device under test on the subjects finger and follow the Instructions For Use (IFU).
14. Wait at least 60 seconds and then take the initial baseline device-under-test blood pressure determination. A third observer will record the data for the device-under-test and the reference values from the auscultators insuring that no pair differ more than 4 mmHg. These baseline data points shall not be used in the accuracy determination.
15. Make sure the previous reading of the device-under-test is cleared prior to the next reading.
16. For each subsequent blood pressure determination, wait at least 60 seconds between the readings.
17. The observers will start with the reference sphygmomanometer, then device-under-test, alternating until three valid paired blood pressure determinations are completed. The final reading should be on the reference sphygmomanometer. Make sure to wait at least 60 seconds between each of the readings.
18. The reference blood pressure determinations prior to the test device and post the test device will be averaged for the actual reference blood pressure determination of comparison.
19. Record each blood pressure determination and the pulse rate on the Case Report Form.
20. A maximum number of attempts for the subject is 8 paired determinations.
21. After three valid test-reference pairs are completed, the cuff will be removed.

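### Do the two descriptions of the two-pair allowance leave the analysed set undetermined?

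*Combined protocol and SAP*

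**What the plan says.** All references are to the combined protocol and SAP.

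- **Method** (Design of the Clinical Investigation). Observer disagreement removes a reading: "Any pair of observers' determinations with a difference greater than 4 mmHg shall be excluded". Further pairs are then taken, up to eight. The section continues "In some cases, it may be that only 2 valid paired readings are achieved" and "This protocol allows for up to 10% of the subjects to have 2 valid paired observations". It names no cause for the shortfall and does not ask that the two pairs be adjacent.
- **Statistical Considerations.** A whole-subject exclusion comes first: "All data from a subject shall be excluded if any two reference systolic blood pressure determinations differ by more than 12 mmHg", with a matching 8 mmHg limit for diastolic pressure. Next comes "If an individual subject is unstable during the period of the test, two valid consecutive determination pairs may be used". The cap follows, opening "No more than 10% individual subjects may have fewer than three valid", with additional subjects to make up any shortfall.
- **Procedure.** Step 14 says of the baseline readings "These baseline data points shall not be used in the accuracy determination". Step 18 averages the reference readings before and after each device reading. Step 20 reads "A maximum number of attempts for the subject is 8 paired determinations".
- **Summary Overview** repeats the 90% rule with neither condition.

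**The concern.** Both sections describe one allowance under one cap, yet only Statistical Considerations mentions instability or consecutive pairs. Instability is not defined in these documents. The only numeric stability limit is the 12/8 rule one sentence earlier, and the text does not say whether the two-pair sentence is an exception to it or operates after it. Criteria 1 and 2 are fixed limits computed on the analysed set, so a membership rule that needs judgement could in principle move a result near a limit. The apparent clash is a subject within 12/8 with two non-adjacent valid pairs: admitted by the Method section and, on a strict reading, not by Statistical Considerations.

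**Working it through.** **1. The plan's own figure.** 85 subjects × 3 pairs = 255, as stated. If k subjects give two pairs, N subjects give 3(N − k) + 2k = 3N − k pairs. The cap allows k = 8 for N from 85 to 89. N = 85 gives 247, N = 87 gives 253 and N = 88 gives 256. So 88 subjects meet the minimum with the allowance fully used, which agrees with the provision for additional subjects.

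**2. The rules applied case by case.**

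| Subject | Method | Statistical Considerations | Outcome |
|---|---|---|---|
| Beyond 12/8 | silent | must be excluded | out |
| Within 12/8, stable, two valid pairs, adjacent or not | admitted | instability sentence does not apply; counts toward the cap | in |
| Within 12/8, unstable, two adjacent pairs | admitted | may be used | in |
| Within 12/8, unstable, two non-adjacent pairs | admitted | not covered by the permission | open |

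The 12/8 rule is mandatory and the instability sentence is permissive, so the exclusion acts first. The word *consecutive* applies only to unstable subjects, and the cap sentence carries neither condition. One row of four is open.

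**3. How many subjects could be in the open row.** The documents give no failure rate for the 4 mmHg check, so let an assumed share q of reference readings fail independently, with up to nine reference readings (eight pairs).

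*Model A:* a failed reading spoils both adjacent pairs and testing continues until three valid pairs. Enumerating all sequences:

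| q | P(exactly two valid pairs) | of 88 | share non-adjacent | non-adjacent, of 88 |
|---|---|---|---|---|
| 5% | 0.12% | 0.1 | 57% | 0.06 |
| 10% | 0.92% | 0.8 | 55% | 0.45 |
| 20% | 5.86% | 5.2 | 52% | 2.7 |

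*Model B:* a failed reading is repeated before the next device reading. Two pairs then means exactly three valid readings among nine: C(9,3)(1 − q)³q⁶. At q = 20% this is 84 × 0.512 × 0.000064 = 0.28%, or 0.24 of 88, and the pairs are always adjacent, so the open row is empty.

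The plan does not say which model holds. Model A's last column is an upper figure, because it treats every non-adjacent two-pair subject as unstable.

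**4. Effect on Criterion 2.** If k of 88 subjects have mean errors with r times the SD of the rest, at the same mean error, s_m is multiplied by √(1 + (k/88)(r² − 1)). Table 1 allows 6.65 at a mean error of 2.0. Dividing 6.65 by the factor gives the s_m without these subjects above which the verdict could change:

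| r | k = 3 | k = 8 (cap) |
|---|---|---|
| 1 | no effect | no effect |
| 1.5 | 6.65/1.021 = 6.51 | 6.65/1.055 = 6.30 |
| 2 | 6.65/1.050 = 6.33 | 6.65/1.128 = 5.89 |

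Both r and the mean error are assumed. Nothing in the documents ties observer disagreement to larger device error, so r = 1 is as defensible as the others. Criterion 1 was not calculated.

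**5. If the order against 12/8 were reversed.** With assumed within-subject reference SDs (systolic/diastolic) of 2/1.5, 3/2 and 4/3 mmHg and independent normal readings, 0.1, 4.8 and 35% of subjects exceed 12/8 on four readings. About 0.1, 3.3 and 20 of 88 exceed it but still hold two adjacent pairs within it, of whom the cap would admit at most 8. These subjects enter only if a mandatory exclusion is disregarded, so they do not measure the wording gap.

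**The case for a change.** The strongest case for a change is that pass/fail limits deserve a set defined without judgement. Instability has no definition, its use is optional, and nobody is named to judge it, while under Procedure step 14 one third observer records both device and reference values. The cap sentence in Statistical Considerations also sets no floor of two pairs, whereas the Method section names two. The remedy would be a few sentences, and enrolment is not strained: 88 analysed subjects with 5, 15 or 35% excluded need 93, 104 or 136 enrolled (88/0.95, 88/0.85, 88/0.65, rounded up), below the maximum of 150.

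The difference in wording and the missing definition stand. The claimed contradiction over a stable subject does not, because the stricter sentence says nothing about stable subjects. The order against 12/8 is settled by the mandatory wording. It is also argued that baseline readings, or readings failing the 4 mmHg check, might count toward 12/8; one baseline reading would raise the exclusion rates in step 5 of the working to 0.2, 7.4 and 47%. Step 14 sets baseline readings apart from the accuracy determination and the Method section removes failed readings, so the ordinary reading leaves both out. The plan says it follows the cited standard, which may define instability; that cannot be checked here.

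**Conclusion.** No change to the plan follows. This is missing detail that a competent analyst fills in one sensible way: apply 12/8 first, admit two-pair subjects up to 10%, and replace the lost pairs. The open case is an unstable subject within 12/8 whose two valid pairs are not adjacent. At most it concerns under half a subject of 88 when 10% or fewer of reference readings fail the observer check, and 2.7 when 20% fail. It concerns none if failed readings are repeated on the spot. The minimum of 85 subjects and 255 pairs is unaffected, no bias is shown, and a Criterion 2 verdict could move only for a device already near its limit and only if these subjects have larger errors than the others. The counts rest on assumed failure rates and retake procedures and the Criterion 2 thresholds on an assumed r and mean error, since the documents supply none of these. The case-by-case reading needs no such assumptions. Aligning the wording would be tidy, but it would write down definitions and would not put a better rule in place.

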**Table 1 — Averaged subject data acceptance (criterion 2)**

$\bar{x}_n$	Maximum permissible standard deviation, $s_m$ , as function of mean error, $\bar{x}_n$ mmHg									
	0,0	0,1	0,2	0,3	0,4	0,5	0,6	0,7	0,8	0,9
$\pm 0,$	6,95	6,95	6,95	6,95	6,93	6,92	6,91	6,90	6,89	6,88
$\pm 1,$	6,87	6,86	6,84	6,82	6,80	6,78	6,76	6,73	6,71	6,68
$\pm 2,$	6,65	6,62	6,58	6,55	6,51	6,47	6,43	6,39	6,34	6,30
$\pm 3,$	6,25	6,20	6,14	6,09	6,03	5,97	5,89	5,83	5,77	5,70
$\pm 4,$	5,64	5,56	5,49	5,41	5,33	5,25	5,16	5,08	5,01	4,90
$\pm 5,$	4,79	—	—	—	—	—	—	—	—	—
EXAMPLE For mean error of $\pm 4,2$ , the maximum permissible standard deviation is 5,49.										

## Monitoring Arrangements

Clinimark [name], USA Site 001	TITLE: Multiparameter Monitor Non-Invasive Blood Pressure Validation Study Clinimark Study ID#: PR2019-329 Principal Investigator: [name]	DOCUMENT NUMBER PR# 2019-329 SHEET 12 of 22	REV 1
---	--	---	-----------------

A Clinimark Independent Monitor (Louisville, CO USA) will provide all monitoring. The Monitor shall be responsible for maintaining a record of the findings, conclusions and actions taken from the results of monitoring the study ensuring that:

The monitoring requirements for an NSR device study is identified in 21 CFR 812.2(b) *Abbreviated requirements*. For monitoring an NSR device investigation, the requirement is to comply with 21 CFR 812.46 with respect to monitoring investigations: (a) Securing Compliance, (b) Unanticipated adverse device effects, (c) Resumption of terminated studies

- Compliance to the signed agreement between the Investigator and sponsor
- The study follows the protocol and any amendments that apply
- Compliance to any conditions of the approval imposed by the IRB or FDA

Additionally:

- The conditions for the study continue to be acceptable
- Accurate, complete, and current records are maintained and required reports are written
- Any adverse effects are documented and reported to the Sponsor and IRB as appropriate
- Monitor activities may include for example: performing source data verification and requesting corrections to feedback forms where potential inconsistencies or missing values are identified.
- Findings of non-compliance or required modifications are reviewed with the investigator and the Sponsor, and is presented in a written report to both
- Providing a Monitoring Report at the end of the Clinical Investigation

### **Monitoring Plan:**

- 1) Informed Consent
  - Verify that the consent form was signed prior to any study procedures being conducted
  - Verify that the staff conducting the consent is listed for approval on the Delegation of Authority Log
  - Ensure that the consent process is documented.
- 2) Subject Eligibility
  - Verify that the subject meets the inclusion criteria and none of the exclusion criteria.
- 3) Baseline Data
  - Verify demographic information with the health assessment short form
  - Check that informed consent time and date is prior to start of the procedure
- 4) Verify all CRFs are completed
- 5) Adverse Events
  - Verify that Adverse Events and Serious Adverse Events / UADEs are being reported accordingly to the IRB and Sponsor in the required timeframe and their respective reporting requirements.
- 6) Protocol Deviations
  - Verify that Protocol Deviations are being reported accordingly to the IRB and Sponsor in the required timeframe and their respective reporting requirements.
- 7) Device Deficiencies
  - Verify that Device Deficiencies are being documented and reported accordingly to the IRB and Sponsor in the required timeframe and their respective reporting requirements.
- 8) Ensure the Trial Master File is complete.

### **Data and Quality Management / Confidentiality**

A checklist will be maintained identifying the contents of the Project folder PFC#2019-329  
The subject's name and signature will be recorded on the Informed Consent, Health Assessment Form, Assent Form (if applies) and a subject participation list. The data collection form will only use a

Clinimark [name], USA Site 001	TITLE: Multiparameter Monitor Non-Invasive Blood Pressure Validation Study Clinimark Study ID#: PR2019-329 Principal Investigator: [name]	DOCUMENT NUMBER PR# 2019-329 SHEET 13 of 22	REV 1
---	---	--	-----------------

subject number and initials for the day of the test along with subject demographics. A name will not be recorded on the data collection form.

Records identifying the subject's name will be kept in a secured location with either a locked file or locked door. Access to these files will be on a limited basis. Potential reviewers of this information include: Clinimark representatives collecting the information and conducting the study, Medical Director for Clinimark, the U.S. Food and Drug Administration (FDA), Department of Health and Human Services (DHHS) agencies, Governmental agencies in other countries, Salus Institutional Review Board and representatives of the sponsor. This group may use the information to conduct independent audits and reviews to verify compliance of the regulatory requirements for these studies but not copy the information.

Data files stored electronically will be associated with a subject based off of subject #, date and by filename recorded on the data collection forms. The original device electronic data files will be preserved in its original form. Data analysis will be performed as a separate electronic file.

Data files, data collection records with subject demographics and subject number may be additionally copied, reviewed and supplied to the commercial sponsor for the study or Contractors associated with Clinimark for data analysis purposes.

There is no current plan to publish this research in scientific journals or present at medical meetings. The subject identity will not be disclosed if the decision to publish is reversed.

All study records will be stored for at least 2 years post the release of the product or project cancellations.

## **Records - Study Documentation**

### **Study procedure**

PR2019-329- IRB Approved Study protocol

### **Subject Documents**

IRB Approved Informed Consent Form (Adult)

Health Form (Clinimark Control # F2000-001-040 REV 1)- Health Assessment-Short Form

### **Study Conduct Documents**

CRF2019-329- Case Report Forms

### **Case Report Forms**

To ensure the quality and integrity of the data, it is the responsibility of the Investigator(s) or designee to complete the Case Report Forms (CRFs) for each subject who is enrolled to participate in this study.

In some cases the CRFs will also be the source document for some information that is not directly collected in the Health Assessment Form. The following information will be recorded on the CRF as appropriate:

- Study date, Subject ID#, Subject Initials, and Relevant Subject Demographics,
- Evidence that informed consent was signed and dated prior to the subject participating in the study
- Information for Subject Inclusion or Exclusion to the study
- Device usage and cuff placement on the subject
- Baseline heart rate
- Baseline blood pressure
- Annotations and observations used in the data analysis
- Protocol deviation reporting
- Adverse Events reporting

Clinimark [name], USA Site 001	TITLE: Multiparameter Monitor Non-Invasive Blood Pressure Validation Study Clinimark Study ID#: PR2019-329 Principal Investigator: [name]	DOCUMENT NUMBER PR# 2019-329 SHEET 14 of 22	REV 1
---	--	---	-----------------

- Study termination

A black or blue pen will be used to record data on the data collection forms. Recorded information should be legible and completed. Erroneous entries should be crossed out, corrected with the change, initialed and dated by the individual making the correction. The Investigator(s) or designee will sign and date at indicated places on each page of the data collection form. The Protocol Deviations Reporting can be signed and dated by the designee only if there are no deviations, otherwise the Sub-Investigator or Investigator should review, sign and date. The Adverse Events Reporting should be signed and dated by the designee and a Sub-Investigator or Investigator. The Principal Investigator needs to review, sign and date all serious adverse events. The Investigator or designee will provide a final signature indicating that a thorough inspection of all subject data has been performed and will thereby certify the contents of the forms. The Investigator's Certification Statement will disclose the overall documentation, study oversight and certification of the study.

